## Section 9.2 IND Drugs

### 9.2) For each drug requiring an IND, provide the drug name, dose, and route of administration

Name: Oxytocin

Trade Name: Pitocin

Description: Peripherally, oxytocin causes the contraction of uterine smooth muscle and of the myoepithelial cells within the mammary gland. In the central nervous system, oxytocin is a modulator of social behaviors, facial recognition, fear, anxiety, and trust. Oxytocin is metabolized by hepatic oxytocinases and disposed by biliary and renal excretions.

Molecular Formula: C43H66N12O12S2

Chemical Structure: Cysteine - tyrosine - isoleucine - glutamine - asparagine - cysteine - proline - leucine - glycine (CYIQNCPLG)

Pharmacologic Class: Neuropeptide

Formulation: Each 1.5 mL vial contains 60 units/mL (.1056 mg/mL).

Route of Administration: Intranasal

Storage and Stability: Refrigerator (2°-8°C)

Clinical studies of the effects of intranasal oxytocin administration have been conducted successfully worldwide for more than 10 years. In the US, intranasal administration of oxytocin is used in clinical studies, similar to the proposed one, in two possible routes: 1. Under an IND from the FDA. 2. Under an IND exemption (described here; Kubzansky et al 2009).

We are seeking an exemption from IND filing requirements for a clinical investigation of a drug product that is lawfully marketed in the United States under exemption category 1. The intention of the investigation is NOT to report to the FDA as a well-controlled study in support of a new indication for use or to be used to support any other significant change in the labeling for the drug. The drug that is undergoing investigation is lawfully marketed as a prescription drug product, and the intention of the investigation is NOT to support a significant change in the advertising for the product. Lastly, the investigation does NOT involve a route of administration or dosage level or use in populations or other factor that significantly increases the risks (or decreases the acceptability of the risks) associated with the use of the drug product.

To our knowledge, oxytocin was never found to have been withdrawn from investigation or marketing in any country due to any safety or efficacy related reasons. The application of the substance is considered safe for administration to human subjects under the conditions of the study since intranasal oxytocin at this dosage is known from decades of use to be safe and well tolerated, as evidenced by their routine usage in protected patient populations, such as nursing mothers (The nasal form of Oxytocin – Syntocinon, manufactured by Novartis Pharma – is listed in the FDA website as being used routinely from the 1962 until 1995). The only contraindications are known hypersensitivity reactions to oxytocin. The dosage proposed in this study conforms to clinical doses and have been used previously in normal and clinical volunteers for research studies by others and ourselves, including Collaborator [name] in a VA-funded study. Any side effects for this application form are rare, and no serious side effects have been recorded for intranasal application of up to 60 IU OT (Epperson et al. 1996). Nausea and vomiting, and transient cardiac arrhythmias have been described rarely. In addition, anaphylactic reactions are described in the data sheet, although the medical literature only contains case reports related to intravenous application of OT.

Furthermore, a previous IND exemption (#75429) states, "Intranasal oxytocin has previously been approved for marketing in the United States from March 20, 1962 until its withdrawal from the market on August 7, 1997." The Federal Register notice issued on that date [Federal Register, Vol. 62, No. 152, Docket No. 97N-0326, pp. 42575 – 42577] clearly states that this withdrawal was at the request of the manufacturer, because the drug was no longer being marketed. No safety reasons were cited in connection with the withdrawal. The intranasal form of oxytocin remains on the market outside of the United States.

Finally, this investigation is conducted in compliance with the requirements for review by an IRB and with the requirements for informed consent. This investigation is also conducted in compliance with the requirement that the investigation is not intended to promote or commercial the drug product.

Since this protocol involves weekly doses of a hormone that has been shown to have minimal side effects, a short half-life in adults, and a good safety profile in adults even with chronic administration (Horta et al., 2020), an IND exemption appears to be justified.

9.2b) Enter the IND Number:

9.2c) Identify who/what entity holds the IND and the status of the IND

9.2d) Identify the storage and security of the drug. For example, at the VASDHS, state "The investigational drug will be stored in the Research Pharmacy in accordance with 119-SOPP-10/151-SOPP-38." Also, identify whether the drug is a controlled substance.

Oxytocin will be compounded, refrigerated and shipped directly to the participant's home with administration and refrigerated storage instructions by Harbor Compounding Pharmacy in Costa Mesa, CA with operational support from the VA Pharmacy, which will be responsible for sending prescriptions and documenting the medication in Veterans' medical charts.

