### PARTICIPANTS:

Participants will be 20 Veteran couples (i.e., 20 Veterans and their 20 partners; 40 individuals total) who are interested in receiving couples therapy for PTSD and relationship problems. Couples of all genders, ages, and ethnicities will be included. Participants must enroll and participate together as a couple; if one partner is not interested in participating, the couple will not be enrolled, and referrals for alternative individual services will be offered.

**Inclusion criteria** for the study will require one member of the couple be a Veteran enrolled in the San Diego VA Healthcare System with a Posttraumatic Stress Disorder Checklist-5 score of > 33, indicating a likely PTSD diagnosis. Veterans must agree not to receive other individual or conjoint psychotherapy for PTSD during participation in the study. If already on psychoactive medication prior to study referral, Veteran participant must remain on a stable psychoactive medication regimen for at least 45 days.

**Exclusion criteria** will be acute suicidality; psychosis; active substance use disorder; severe ongoing medical problems, including heart disease and neuroendocrinological disorders (e.g., diabetes); uncontrolled hypotension (systolic blood pressure <100 mm Hg) or hypertension (>160/100 mm Hg); pregnancy, delivery in the past 6 months, or current breastfeeding; or severe intimate aggression reported by either partner (established with validated measures). A list of alternative resources will be provided to ineligible participants.

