## Section 10 - Human Subjects

**10) Describe the characteristics of the proposed subject population. Include age, gender, ethnicity, and health status as appropriate. Note: Data about people are still considered "human subjects" by the IRB, so even if you do not intend to contact the patients whose charts you will review, you still describe the characteristics related to the subjects whose charts you will review.**

- Provide inclusion and exclusion criteria as appropriate. Provide a statement how non pregnancy is confirmed if pregnancy is an exclusion criteria.
- For multisite studies, provide the total number of subjects from all sites and include description of the local site's role as a coordinating center if applicable.
- Indicate the number of VA participants to be studied.
- Indicate the estimated number of consented subjects that will fail the screening process, if any.

A total of 40 participants will be enrolled: 20 Veterans plus their partners (who may or may not also be Veterans). Therefore, between 20 and 40 VA participants will be studied.

Inclusion criteria for the study will be a veteran enrolled in the San Diego VA Healthcare System with a Posttraumatic Stress Disorder Checklist-5 score of > 33, indicating a likely PTSD diagnosis. Veterans must agree not to receive other individual or conjoint psychotherapy for

PTSD during participation in the study. If already on psychoactive medication prior to study referral, Veteran participant must also be on a stable psychoactive medication regimen for at least 45 days.

Exclusion criteria will be acute suicidality; psychosis; active substance use disorder; severe ongoing medical problems, including heart disease and neuroendocrinological disorders (e.g., diabetes); uncontrolled hypotension (systolic blood pressure <100 mm Hg) or hypertension (>160/100 mm Hg); pregnancy, delivery in the past 6 months, or current breastfeeding; or severe intimate aggression reported by either partner (established with validated measures). Because the effects of oxytocin on pregnancy outcome are well known, pregnant and lactating females will be excluded from the trial. We will instruct participants who are able to become pregnant to use appropriate forms of contraception, and we will instruct them to perform urine pregnancy tests at baseline and weekly during treatment before self-administration of oxytocin if a Veteran participant is considered able to become pregnant.

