## Section 12.10 HIPAA Waivers and Alterations

**12.10a) Describe the purpose/nature of the HIPAA waiver or alteration and list specifically, what identifiers and health information are being requested under the waiver/alteration and identify whether the waiver is for access, use, and/or collection of this information.**

All referrals for potential participants will come directly from clinical providers after Veterans have indicated interest in the study. For Veterans who indicate interest, [name] will be tagged on the CPRS note. [name] will contact the couple only after they indicate to their clinical provider a desire to be contacted (which will be documented on the Veteran's CPRS note), to further describe the study, screen for eligibility, and schedule the couple for a pre-treatment assessment session.

Because we will screen Veteran patients for eligibility over the phone, we are requesting a partial HIPAA/consent waiver for screening. This will help us eliminate unnecessary burden for those couples who may not qualify for the study by not scheduling a full assessment visit, and instead facilitating efficient referrals to other appropriate care. At this screen, we will collect the following data for the veteran partner: gender, name (first and last), address, phone contact numbers, and social security numbers. With the waiver we will utilize the following for looking at prospective participants when added as signers to patient CPRS notes: First and Last name, last four of the social security number, address, and phone number.

Pre-eligibility screening questions will include: age; Veteran status; scheduling conflicts and technology availability; whether or not the individual has been told by a medical provider that he or she has a psychotic disorder or a neurocognitive disorder; suicide attempts in the past year; pregnancy or recent birth; exclusionary medical condition; and intimate partner violence in the relationship. See Phone Screen attachment. These screening procedures match currently approved CBCT trial (protocol # H150181) as well as OurRelationship.com Pilot (protocol # H190163).

A HIPPA waiver is also necessary to allow for the disclosure of prospective subjects' names and email addresses to DocuSign for the purposes of emailing them the consent and HIPPA forms

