If participants do experience notable distress, they will be provided with contact information for licensed psychologists on study staff, including the PI, and follow-up referrals as appropriate. In addition, they will be given access to a 24-hour crisis psychiatry telephone service. However, our prior research suggests that data collection using the aforementioned procedures can be conducted without undue psychological distress or exacerbation of symptoms among participants. This experience includes substantial research with distressed couples and with technology-mediated interventions. In the event of an Adverse Event (AE), Serious Adverse Event (SAE), or Unanticipated Problem Involving Risks to Subjects or Others (UPR), all notification procedures outlined in the Data Safety and Monitoring Plan section will be followed.

Steps to protect against risk associated with intranasal oxytocin administration will be taken. During informed consent, participants will be informed about the potential side effects of intranasal oxytocin. Participants will not be enrolled unless the study psychiatrist, [name], concurs that no oxytocin-related exclusion criteria are met and the Veteran participant is eligible. Participants will self-administer intranasal oxytocin while being monitored on video by research staff who have ready access to clinicians who can consult on the need for emergency care, if necessary. They will be closely monitored by the research team after each drug administration. Women who are pregnant and lactating women will be excluded from the trial. We will instruct participants who are able to become pregnant to use appropriate forms of contraception, and we will instruct them to perform urine pregnancy tests at baseline and weekly during treatment before self-administration of oxytocin if a Veteran participant is considered able to become pregnant.

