## Section 18 - Risk/Benefit Analysis

### 18) Discuss why the risks to subjects are reasonable in relation to the anticipated benefits to subjects and in relation to the importance of the knowledge that may reasonably be expected to result.

Risk from participating in B-CBCT augmented with intranasal oxytocin is relatively minor in comparison with the potential benefits to relationship quality and PTSD symptoms to be gained by Veterans and their partners in this study, and is not anticipated to be any greater than risks they may encounter during standard clinical care. This investigation may help subjects manage the symptoms and functional impairment associated with PTSD and will provide valuable knowledge about the treatment of PTSD in Veterans. Furthermore, it may also help couples manage and improve relationship problems and associated functional impairment and will provide valuable knowledge about the treatment of relationship distress in Veterans with PTSD. Thus, the risk benefit ratio warrants this study being conducted.

This conclusion is supported further by the protection procedures in place to address any discomfort caused by the assessment or treatment to Veterans and partners. There is minimal risk associated with gathering information about emotional symptoms and taking part in a brief treatment for such symptoms based on an evidence-supported, manualized intervention. There are no aspects of this study that place participants at additional physical, psychological, social, legal or other risk outside of routine medical and mental health care. Risks associated with oxytocin consumption are mitigated by excluding pregnant women, conducting weekly pregnancy tests for Veteran participants who are able to become pregnant, and weekly questionnaire completion regarding any side effects of the oxytocin. Finally, we are mitigating the current risk of COVID-19 exposure by allowing participants to remain in their homes by using entirely virtual (telehealth, web, and phone) procedures for study enrollment and consent, intervention, and assessment. This study uses the existing VA telehealth infrastructure, including secure VVC telehealth appointments and Webex.

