Electronic research data will include audio recordings of B-CBCT sessions as well as responses on self-report assessment surveys. Research data will be collected by hard copy or by phone and will be entered into an electronic data set stored on VA secure local research servers accessible only by authorized users on password-protected computers.

In terms of participant safety monitoring, each participant will be given the telephone number of the PI and study clinician during the consenting process. Participants will be encouraged to call the PI or notify study staff if they experience significant distress from participating in the study. Any study staff will contact the PI about any participant who appears or reports significant distress related to study participation. All such participants will then be contacted personally by the PI and, in cases where the distress is extreme, the PI will decide upon and provide needed services or referrals. The study's exclusion and inclusion criteria provide additional clinical safeguards by identifying appropriate participants for this treatment and excluding high risk patients (i.e., suicidal/homicidal ideation, domestic violence, active SUD, pregnancy /breastfeeding, and hypertension).

This study will include a Data Safety and Monitoring Plan (DSMP) that will be developed in accordance with the National Institutes of Health (NIH) Office of Human Research Protection (OHRP) to assure the appropriate clinical safety monitoring of study subjects participating in this study. Recruitment and safety data are monitored according to the schedule established by the monitoring board, generally every 4-6 months for intervention studies. Quality control and assurance of data entered into the database is discussed above as part of Protections Against Risk. Missing data will be considered as part of the plan for statistical analysis. This study will not include a Data Safety Monitoring Board.

**27.b) Entry of a CPRS Research Informed Consent Note is required when subjects will be admitted as inpatients or treated as an outpatients for research and the study involves research medical care or may affect medical care.**

- *If a Research consent Note is required, then a Research Progress Note should also be entered for each procedure or intervention.*

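### Known hypersensitivity to oxytocin, which the protocol itself calls a contraindication, is in neither exclusion list and in no described screening step (minor: two PCL-5 entry cut-offs)

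*Protocol*

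**What the plan says.** Section 9.2 (IND Drugs), in its safety argument for an IND exemption, says: "The only contraindications are known hypersensitivity reactions to oxytocin". The same paragraph notes that "anaphylactic reactions are described in the data sheet", while limiting the published case reports to intravenous use.

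Eligibility is set out twice. Section 9 (Participants) excludes, among other things, "severe ongoing medical problems, including heart disease and neuroendocrinological disorders (e.g., diabetes", together with blood-pressure limits, pregnancy, recent delivery, breastfeeding and severe partner aggression. Section 10 repeats the list, beginning "Exclusion criteria will be acute suicidality; psychosis; active substance use disorder; severe ongoing medical problems". Neither list has a hypersensitivity or allergy item.

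The screening steps are these. Section 12.10 gives the phone-screen topics, which end with "pregnancy or recent birth; exclusionary medical condition; and intimate partner violence in the relationship". In Section 9 the prescriber verifies eligibility before writing the prescription. Section 15 allows enrolment only if the study psychiatrist "concurs that no oxytocin-related exclusion criteria are met and the Veteran participant is eligible".

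On the PCL-5, the inclusion criteria in Sections 9 and 10 ask for a score above 33. The Data Collection part of Section 9 admits Veterans scoring 33 or more, and defines probable PTSD in the same way.

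**The concern.** A contraindication should appear among the exclusion criteria, because those are what the people screening and prescribing apply. Here it appears only in the regulatory drug description. The drug is shipped to the Veteran's home and self-administered there while staff watch by video. For a reaction that is already known, the effective control is to keep the person out before the first dose; observation and side-effect questionnaires act during or after exposure.

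The protocol handles its other contraindications differently. Section 14 says oxytocin is contraindicated in pregnancy and lactation. Both are carried into the exclusion lists, and pregnancy also into the phone screen and weekly testing. That contrast suggests the hypersensitivity omission is an oversight rather than a choice.

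The PCL-5 discrepancy is much smaller. A Veteran scoring exactly 33 is eligible under one sentence and ineligible under another.

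**Working it through.** **Hypersensitivity.** No arithmetic applies. The check sets the contraindication in Section 9.2 against each place where an unsuitable participant could be identified or where exclusions are summarised.

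| Place in protocol | What it covers | Hypersensitivity named? |
|---|---|---|
| Section 9, Participants (exclusions) | suicidality, psychosis, substance use, severe medical problems, blood pressure, pregnancy and breastfeeding, aggression | No |
| Section 10 (exclusions) | same list | No |
| Section 9, Data Collection (pre-enrolment measures) | PTSD, suicidality, partner violence, alcohol | No |
| Section 9.8 (questionnaire list) | instruments, pregnancy test, side-effect form | No |
| Section 12.10 (phone screen) | includes a general item on exclusionary medical conditions | No |
| Section 9, Description of Intranasal Oxytocin (prescriber) | verifies study eligibility | No |
| Section 15 (psychiatrist) | concurs that oxytocin-related exclusion criteria are not met | No |
| Section 18 (oxytocin risk mitigation) | "Risks associated with oxytocin consumption are mitigated by excluding pregnant women, conducting weekly pregnancy tests for Veteran participants who are able to become pregnant", and the weekly side-effect questionnaire | No |
| Section 27 (summary of exclusions) | "excluding high risk patients (i.e., suicidal/homicidal ideation, domestic violence, active SUD, pregnancy /breastfeeding, and hypertension" | No |

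Three of these steps are general enough to pick up an allergy in practice: the phone-screen item, the prescriber's verification and the psychiatrist's concurrence. Each works by reference to what is exclusionary or what makes a Veteran eligible, and the lists that define those terms leave this condition out. The closest criterion is severe ongoing medical problems. Its examples are heart disease and neuroendocrine disorders, so a past drug reaction in someone who is now well does not clearly fit.

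Exposure if the gap is not caught: 8 sessions × one 40 IU dose before each = up to 8 home doses per affected Veteran.

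The word *only* in Section 9.2 also conflicts with Section 14 on pregnancy and lactation. Both are already excluded, so nobody's eligibility changes.

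**PCL-5 cut-off (minor).** The two rules differ only at a score of 33. The documents give no score distribution, so one is assumed: whole-number scores 0–80 following a discretised normal, for the screened pool before the cut-off is applied, with mean 40–50 and SD 12–15.

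- Share affected: p = P(score = 33) / P(score ≥ 33)
- Expected number among 20 Veterans: 20p
- Chance of at least one: 1 − (1 − p)^20

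For mean 40 and SD 12, P(33) = 0.0281 and P(≥ 33) = 0.7342, so p = 0.0281 / 0.7342 = 0.038.

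| Mean / SD | p | 20p | Chance of at least one |
|---|---|---|---|
| 40 / 12 | 0.038 | 0.76 | 0.54 |
| 40 / 15 | 0.035 | 0.69 | 0.51 |
| 45 / 12 | 0.024 | 0.47 | 0.38 |
| 45 / 15 | 0.024 | 0.49 | 0.39 |
| 50 / 12 | 0.013 | 0.26 | 0.23 |
| 50 / 15 | 0.016 | 0.33 | 0.28 |

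These assumptions imply a mean of 45.3 to 52.7 among Veterans scoring 33 or more.

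**The case against.** The strongest reply is that a clinical check already exists. A prescriber verifies eligibility and writes each prescription, a VA psychiatrist must agree before anyone is enrolled, and the VA Pharmacy documents the drug in the chart. For harm to follow, a physician would have to prescribe a drug to someone with a known reaction to it. The phone-screen form is an attachment outside these documents and may contain an allergy question. The risk also looks low: Section 9.2 reports no serious side effects intranasally up to 60 IU, and Section 14 cites over 900 participants given 40 IU without a severe adverse event. Sections 18 and 27 are summaries rather than eligibility procedures, so their silence is weak evidence.

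Much of this is fair. The likely number affected among 20 Veterans is small, though the documents give no figure, and Sections 18 and 27 add little. It does not remove the inconsistency. Nothing in the text requires anyone to ask about a previous reaction, and the checks relied on refer to criteria that omit it. The concern is limited to what the protocol describes.

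On the PCL-5, a ≥ sign may have been lost when the text was extracted, and the wording in Data Collection is clear enough for a reader to infer the intended rule. That is why the point is minor.

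**Conclusion.** The concern holds. As written, the eligibility rules would admit a Veteran with a condition that the protocol itself lists as a contraindication, for up to eight home doses. It affects only Veterans with a known reaction; no count can be given without a prevalence, and the absolute risk is probably low. The conclusion rests on the protocol text alone and would soften if the phone-screen form already asks the question. It should be corrected because it concerns participant safety and the correction costs almost nothing.

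The PCL-5 conflict is real as the text stands but minor: 1.3% to 3.8% of Veterans at or above 33, or 0.26 to 0.76 expected among 20, with a 23% to 54% chance of at least one, all under the assumed distributions. No effect on any estimate or analysis is claimed for either point.

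**What to change.** 1. Add known hypersensitivity to oxytocin to the exclusion criteria in Section 9 (Participants) and Section 10.
2. Add one question on previous reactions to oxytocin to the phone screen described in Section 12.10, and name the condition in the psychiatrist's eligibility check in Section 15.
3. Remove *only* from the contraindication sentence in Section 9.2, or add pregnancy and lactation there, so that it agrees with Section 14.
4. Minor: state the PCL-5 criterion as 33 or more in Sections 9 (Participants) and 10, matching Data Collection.

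The cost is a few words in four places for items 1 to 3 (the PCL-5 wording sits in two of those same places) and one screening question. There are no new visits or tests, and the sample size does not change.
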